6.1 Background

Norditropin[®] (NN-220; somatropin; Novo Nordisk A/S, Denmark), a recombinant human growth hormone (rhGH) produced by genetic recombinant technology, is currently the sole approved medication for the treatment of short stature due to NS in France. In October 2020, the Transparency Committee (CT- *Commission de Transparence*) rated the actual clinical benefit (SMR- *Service Medical Rendu*) of Norditropin[®] as “important” and issued a favourable opinion for inclusion of Norditropin[®] on the list of reimbursed proprietary medicinal products in NS children with short stature (< -2 SDS)(1). The CT has recommended that Norditropin[®] treatment be initiated under following conditions:

- After resolution of feeding difficulties associated with (or not) underweight, given that these disorders are common before the age of 2. Thus, clinical data on efficacy and safety should be evaluated in paediatric patients aged at least 3 years.
- After genetic diagnosis confirmation to optimize NS management.
- At the lowest dosage of RCP (0.033 mg/kg/day). The dosage should be tailored to each patient and adjusted every six months based on clinical response (growth velocity and height) and treatment tolerance (IGF-1 monitoring).

6.2 Study Rationale

Given the complexity of NS management and potential risks associated with Norditropin[®] administration, the CT has also advised that Norditropin[®] be solely prescribed by paediatric endocrinologists and that the follow-up of NS children be coordinated by French reference/competence centres of NS (1).

Despite the existing literature documenting the effect of GH therapy on height outcomes, long-term effectiveness and safety data associated with Norditropin[®] treatment is needed. So far, data on use of Norditropin[®] treatment in NS children with short stature remain limited and arise mostly from observational studies with small number of patients and restricted follow-up, notably until adult height. This is of importance when considering that GH therapy should be initiated early, and for a prolonged time. Furthermore, information on quality of life in NS patients remains scarce, while literature has shown that short stature has been associated with lower HRQoL. To our knowledge, no study has specifically assessed the evolution of HRQoL in NS children with short stature and under GH treatment.

Hence, the CT has requested the development of a national registry of NS children with short stature and treated with Norditropin[®] until adulthood. Data should be available within five years. This registry shall provide information on long-term clinical evolution of these patients (e.g adult height and quality of life) and on the safety profile of Norditropin[®] (notably the risk of tumour, effect on

glucose metabolism and cardiac defects). The CT has also recommended that data collection be defined in collaboration with French reference and competence centres.

To respond to the CT request, Novo Nordisk will establish a French registry of NS children treated with Norditropin[®] for short stature to assess the long-term growth evolution and safety of Norditropin[®]. Children will be followed-up for 4 years (with possibility of extension for patients who did not reach adult height) in hospital setting notably in French reference/competence centres specialized in the care of short stature due to NS (the rare endocrine disorders network referred as FIREENDO). This registry also aims to collect data on quality of life, clinical, genetic and other relevant NS characteristics.

A committee of experts (referred as the scientific committee) was constituted to provide support in the data to be collected in the registry. This scientific committee consists of physicians practicing in reference/competence centres of the FIREENDO network.

7 Research question and objectives

The present study has been designed to develop a French registry of children treated with Norditropin[®] for short stature due to NS.

7.1 Primary objective

The primary objective is to describe the long-term change of height in children treated with Norditropin[®] for short stature due to NS over a 4-year period* in routine clinical practice in France.

7.2 Secondary objectives

All secondary objectives (as follows) apply to children treated with Norditropin[®] for short stature due to NS:

- To describe the long-term safety profile of Norditropin[®]
- To describe the socio-demographic and clinical characteristics of patients
- To describe the therapeutic care of patients
 - Describe GH treatment patterns
 - Describe other NS treatments
- To describe the NS in terms of auxological characteristics, diagnosis, and NS comorbidities
- To describe the change in health-related quality of life (HRQoL) of patients and their parents /Legally Acceptable Representative (LAR)

* The follow-up period in this study is 4 years with possibility of extension for patients who did not reach adult height.

7.3 Exploratory objectives

The exploratory objectives are as follows:

- To identify driving factors that are associated with HRQoL
- To identify driving factors that are associated with change in height (SDS) over a 4 year* period

8 Research methods

8.1 Study design

This study is a PASS. This is a non-interventional registry of children treated with Norditropin® for short stature due to NS. This study aims to provide data on long-term growth evolution and safety of Norditropin® as well as HRQoL data. This registry will include the entirety of children treated with Norditropin® for short stature due to NS over the inclusion period. In consequence, this registry will enroll both patients who received Norditropin® before its marketing authorization for short stature due to NS in France and patients who received Norditropin® after its approval.

This study presents both a prospective and retrospective design. Data will be collected for 3 groups of patients:

- Incident patients: Children initiating Norditropin® upon their inclusion in the study.
- Prevalent patients:
 - Children who were already treated with Norditropin® before their inclusion in the study and finished their growth upon their inclusion. For these patients, all data will be collected retrospectively from medical records.
 - Children who were already treated with Norditropin® before their inclusion in the study and who did not finish their growth upon their inclusion. For these patients, data will be collected both retrospectively and prospectively.

HRQoL data will be collected on incident patients only.

The inclusion period will last for 24 months and patients will be followed-up for 4 years with possibility of extension for patients who did not reach AH. This will allow to provide interim results on October 2025 to the HAS.

All information will be collected as per physicians' routine of care and as this study is non-interventional, neither clinical interventions nor laboratory assessments will be imposed as per this protocol.

* The follow-up period in this study is 4 years with possibility of extension for patients who did not reach adult height.

[figure not shown]
For incident patients, a visit schedule is provided based on the standard clinical practice for GH treatment in NS. We anticipate that each child included in this registry sees his/her enrolling physician every 6 months based on recommendations. A total of 9 visits (1 inclusion visit: D0 and 8 follow-up visits: M6, M12, M18, M24, M30, M36, M42, M48) are planned. Each visit will be allowed within one-month visit. However, no follow-up visits will be mandated by this study and the enrolling physician may not strictly comply with the schedule provided if considered as not relevant.

For prevalent patients who finished their growth upon their inclusion, all data will be collected retrospectively from medical records bi-annually from the start of Norditropin®. Visits will be referred to as V1, V2, V3... VX.

For prevalent patients who did not finish their growth upon their inclusion, data will both be collected retrospectively from medical records bi-annually from the start of Norditropin® and prospectively every 6 months following the inclusion visit.

The design of the registry is displayed in [Figure 8-1](#). This is a PASS.

Figure 8-1 Study design

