Start of data collection (FPFV)	March 2022
Last Patient First Visit (LPFV)	March 2024
Last Patient Last Visit (LPLV)	March 2028
Study progress reports	Monthly update during implementation, inclusion & follow-up

Protocol
Study ID: GH-4831
U1111-1264-1805
EU PAS No.: Study not yet registered

~~CONFIDENTIAL~~

Date: 21 February 2022
Version: 10.0
Status: Final
Page: 14 of 58

Novo Nordisk

Milestone	Planned date
Interim report of study results	October 2025
Final report	August 2028

6 Rationale and background

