8.7 Data analysis

8.7.1 Definition of analysis sets

The site populations will be defined as follows:

- Contacted sites: all reference and competence centres in France will be solicited to participate in this study
- Participating sites: all sites that agreed to participate in the study
- Active sites: all sites that included at least one eligible patient

The sites main characteristics (localisation, size) will be compared to ensure that the active sites are representative at the national level.

There are 3 patients population considered in this study:

- Overall population: all patients included in the eCRF,
- Full Analysis Set (FAS): all patients included in the eCRF and meeting all selection criteria. All secondary analyses will be performed on FAS.

- Growth Analysis Set (GAS): all patients from the FAS for which the primary criteria can be evaluated, i.e. height measurements available until the end of the 5-year follow-up or until NAH is reached, whatever occurs first.

The subgroups of interest for analyses are defined as follows:

- Norditropin[®] treatment duration: depending on age of onset and age at puberty onset, the patients may have shorter or longer time under GH treatment, which may highly influence auxological outcomes
- Mutated gene: PTPN11, SOC2, other

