8.7.2 Statistical methods

A descriptive analysis will be conducted on all study endpoints for which data has been collected both on FAS (GAS for primary endpoint) and per subgroups of interest as long as that the sizes of the subgroups are relevant for statistical estimations.

The following statistics will be provided for quantitative variables: number of patients with non-missing and missing values, mean, standard deviation, median, first quartile (Q1), third quartile (Q3), minimum and maximum value, mode (for discrete quantitative variables with limited variability).

For qualitative variables, the number and proportion of each variable modality will be provided together with the number of missing values. Proportions will be computed based on the population with non-missing data. Missing data will not be imputed or replaced.

Exploratory comparison between study subgroups might be considered. Statistical tests will be based on the type and the variables. All comparison tests will be two-tailed with a standard type 1 error threshold of 5% (significance level).

In order to reach the exploratory objectives, logistic regressions will be implemented to identify factors linked to Norditropin[®] growth evolution (reaching height > -2 SDS) and patients' HRQoL. The clinically relevant explanatory variables will be first tested with univariate regression. The selected variables will be processed in the multivariate regression (backward selection) and the odds-ratio with their 95% confidence interval will be used for interpretation when the variable effect is significant (5% threshold for p-value).

In addition, a mixed model will be developed to explore HRQoL scores evolution over the follow-up. Patient effect will be considered as random effect.

The patients will be enrolled in the study over a variable period limited to 24 months. The probability that a patient is included in the cohort is greater when the patient has a higher number of annual visits. This study design therefore presents several biases related to:

- the heterogeneous duration of patients' inclusion which depends on the activity size of each participating site;

- the probability that a patient is included in the cohort which depends on the frequency of annual visits.

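### The October 2025 interim growth result is tied to the completer set (GAS), which no incident child can enter by then unless already at adult height

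*Protocol*

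**What the plan says.** The milestones (abstract and section 5, Table 1) are: "Start of data collection (FPFV) March 2022"; "Last Patient First Visit (LPFV) March 2024"; "Last Patient Last Visit (LPLV) March 2028"; "Interim report of study results October 2025". Section 8.1 links the inclusion period and follow-up to the interim: "This will allow to provide interim results on October 2025 to the HAS".

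Section 8.7.3, on the interim analysis, contains only a cross-reference to 8.7.2.1 (primary), 8.7.2.2 (secondary), 8.7.2.3 (exploratory) and 8.7.4 (safety). It gives no interim time point, analysis set or data cut of its own.

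Section 8.7.2 assigns the primary endpoint to the GAS and the other endpoints to the FAS. Section 8.7.1 defines the GAS by "height measurements available until the end of the 5-year follow-up or until NAH is reached, whatever occurs first". The abstract gives the same rule with 4 years and adult height.

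The start of the clock is not settled. The primary endpoint (Table 2) runs from the start of Norditropin, while section 8.2.8.2 counts the 4 years of visits from inclusion (D0). The two coincide for incident children, who start treatment at inclusion, but differ for prevalent children.

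**The concern.** Followed as written, the interim applies a 4-year completer rule before any newly treated child can have completed 4 years. The main growth result sent to the HAS would leave out the cohort whose data are wholly prospective and would rest almost entirely on prevalent children, whose earlier heights come from medical records.

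This matters because the Transparency Committee asked for data within five years (section 6.2). Counted from its October 2020 opinion, five years ends in October 2025. The final report, due in August 2028, comes 94 months after that opinion. The interim is therefore the report that answers the request on time, and its primary result should cover the children it can cover.

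**Working it through.** **Inputs**
- First visit March 2022, last first visit March 2024, interim report October 2025, last visit March 2028, final report August 2028 (Table 1).
- One-month visit window (abstract).
- At most 50 eligible incident children; at most 30 prevalent starters per year from 2010 to before 2020, read as 10 years; 30 of 38 sites (79%); 80% included; 80% evaluable; CV 20% (section 8.5).

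**Reproducing the plan's figures**
- Included: (50 + 30 × 10) × 0.79 × 0.80 = 221.2 (plan: 221).
- Evaluable: 221.2 × 0.80 = 177.0 (plan: 177).
- Precision: 1.96 × 0.20 / √177 = 2.95% (plan: 2.95%).
- First to last inclusion is 24 months, and last inclusion to last visit is 48 months. The timeline is internally consistent.

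**Incident follow-up at the interim**
- First child: March 2022 to October 2025 = 43 months. The most generous count, 1 March 2022 to 31 October 2025, is 44.0 months.
- Last child: March 2024 to October 2025 = 19 months.
- The first possible M48 is March 2026, or February 2026 if taken one month early. Under the 5-year wording it is March 2027.
- Assumption: if the data cut precedes the report by 5 months, as the last visit precedes the final report (March to August 2028), the range is 14 to 38 months.

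**Share of incident children past each visit**, assuming uniform accrual over 24 months: (maximum follow-up − visit month) / 24, bounded by 0 and 1.

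| Visit | Cut October 2025 | Cut 5 months earlier |
|---|---|---|
| M12 | 100% | 100% |
| M18 | 100% | 83% |
| M24 | 79% | 58% |
| M30 | 54% | 33% |
| M36 | 29% | 8% |
| M42 | 4% | 0% |
| M48 | 0% | 0% |

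**Size of the loss**
- Incident children expected: 50 × 0.79 × 0.80 = 31.6 included; × 0.80 = 25.3 in the planned GAS, or 25.3/177 = 14%. At the interim they contribute none, apart from any already at adult height.
- Prevalent children, clock from treatment start: at most 300 × 0.79 × 0.80 × 0.80 = 151.7. Precision on the plan's formula is 1.96 × 0.20 / √152 = 3.18%.
- Prevalent children, clock from inclusion: those still growing also have at most 43 months, so only children at adult height remain. The protocol gives no count of these.

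**The case against.** The strongest reply is that an interim in a study with a 4-year endpoint is incomplete by nature, that section 8.1 promises interim results rather than 4-year incident results, and that interim cut-offs and sets are commonly left to the SAP. Section 8.7.2.1 does not itself name the GAS; the link comes from the general text of 8.7.2. This would carry weight if 8.7.3 were silent, but it sends the interim to the final analyses. The explicit deferral to the SAP, in 8.7.2.3, concerns only the exploratory models. Section 8.7.2.1 could also be read as taking the last available height as the end of follow-up, but the GAS condition still decides who is analysed.

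Several stronger conclusions are tempting, and the protocol does not support them:
- *That incident children's growth data are discarded.* The GAS restricts only the primary endpoint. Height velocity, in cm/year and SDS/year, is a secondary endpoint (Table 6) analysed on the FAS. Safety and PedsQL data also reach the interim.
- *That only children who have finished growing are described.* This follows only if the 4 years run from inclusion. From treatment start, still-growing prevalent children with long enough records qualify.
- *That children treated since the favourable reimbursement opinion are omitted.* Those who started between October 2020 and inclusion are prevalent. Counted from treatment start, those who began by October 2021 reach 48 months by October 2025. Their number is not given.
- *That the no-imputation rule in 8.7.2 causes the loss.* A visit not yet due is not missing data.
- *That a full repeated-measures model is needed.* The objective is descriptive. With about 32 incident children and seven post-baseline visits (M6 to M42), an unstructured covariance has 7 × 8 / 2 = 28 parameters. A table by time point is enough.

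**Conclusion.** The point holds in a limited form. By the protocol's own dates and cross-references, no incident child without adult height can be in the interim primary result, under either the 4-year or the 5-year definition. About 25 of the planned 177 evaluable children (14%) are affected. The effect on precision is small, from 2.95% to about 3.18%; the damage is to representativeness, because the headline growth result would be almost wholly about prevalent children.

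The 43-month limit rests only on stated dates and is shorter with an earlier data cut. The counts of 32, 25 and 152 rest on the planning maxima in section 8.5. The 152 is an upper bound that also needs the clock to run from treatment start. If the clock runs from inclusion, the interim primary result shrinks to children at adult height. A reader might infer that the interim would be empty or uninformative on newly treated children. It would not be, because the FAS analyses remain; what is missing is their change in height SDS.

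**What to change.** - In 8.7.3, define the interim growth analysis on the FAS: change in height SDS from the start of Norditropin at each 6-month time point, using all available heights, with the number contributing and a 95% CI, shown separately for incident and prevalent children. A simple mixed model with a random patient effect, of the kind 8.7.2 already plans for quality of life, is optional.
- Keep the completer analysis on the GAS for the final report.
- State whether the 4-year clock for prevalent children runs from treatment start or from inclusion.
- Reconcile the GAS definitions: 4 years and adult height in the abstract, 5 years and near adult height in 8.7.1.

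The cost is a paragraph, two clarifications and a little programming. No new data are needed, since the study flow chart already has six-monthly heights. The drawback is few incident children at the later points: under uniform accrual, 29% of about 32 (roughly 9) at M36 and 4% (about 1) at M42, fewer with an earlier cut. The number contributing must therefore stand beside each estimate.

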8.1.1 Endpoint(s)

All endpoints are assessed during long-term routine use of Norditropin® treatment and apply to children treated with Norditropin® for short stature due to NS.

Assessments at baseline (such as sex, age at start of Norditropin® etc.) and at single time points are included in [8.2.10](#) section.

8.1.1.1 Primary endpoint

Table 2 Primary endpoint

Title of endpoint	Time frame	Unit
Change in height standard deviation score	From start of Norditropin® treatment until end of follow-up	SDS

The change in height in SDS (measured in scores -10 to +10) will be derived from recent national growth chart reference(2).

8.1.1.2 Secondary endpoints

Secondary objective-1: To evaluate the long-term safety profile of Norditropin®.

All drug related adverse reactions (ADR), serious adverse drug reactions (SADR), serious adverse events (SAE) and adverse events (AE) will be recorded and described up to the end of growth development or end of follow-up if earlier. The endpoints related to the secondary objective-1 are listed in [Table 3](#).

Table 3 Secondary endpoints in relation to secondary objective 1

Title of endpoint	Time frame	Unit
Number of adverse drug reactions (ADR)	From start of Norditropin® until end of follow-up	Count of events
Number of serious adverse drug reactions (SADR),	From start of Norditropin® until end of follow-up	Count of events
Number of serious adverse events (SAE)	From start of Norditropin® until end of follow-up	Count of events
Number of adverse events (AE)	From start of Norditropin® until end of follow-up	Count of events

Secondary objective-2: To describe the socio-demographic and clinical characteristics of patients. The endpoints related to the secondary objective-2 are listed in [Table 4](#).

Table 4 Secondary endpoints in relation to secondary objective 2

Title of endpoint	Time frame	Unit
Socio-demographic		
Education	From start of Norditropin® treatment until end of follow-up	NA
School level	From start of Norditropin® treatment until end of follow-up	NA
Educational measures	From start of Norditropin® treatment until end of follow-up	NA
Clinical characteristics		

Title of endpoint	Time frame	Unit
Tanner stage	At all visits	NA
Change in pulse rate	From start of Norditropin® treatment until end of follow-up	Beats per minute
Change in diastolic blood pressure	From start of Norditropin® treatment until end of follow-up	mm Hg
Change in systolic blood pressure	From start of Norditropin® treatment until end of follow-up	mm Hg
Change in corrected QT-interval (Electrocardiogram)	From start of Norditropin® treatment until end of follow-up	msec
Change in echocardiogram parameters	From start of Norditropin® treatment until end of follow-up	mm (Left ventricular interventricular septal maximum thickness in diastole) mm (Left ventricular end diastolic diameter) % (Left Ventricular Fractional Shortening (LVFS)) % (Left Ventricular Ejection Fraction (LVEF)) Cm/s (Diastolic function (Ea)) Cm/s (Diastolic function (Aa))
Change in complete blood count (CBC)	From start of Norditropin® treatment until end of follow-up	g/dL (Haemoglobin-Hb) G/L (White blood cells) G/L (Lymphocytes) G/L (Monocytes) G/L (Platelets)
Change in IGF-1 level	From start of Norditropin® treatment until end of follow-up	ng/ml and SDS
Change in HbA _{1c} level	From start of Norditropin® treatment until end of follow-up	%
Change in fasting insulin level	From start of Norditropin® treatment until end of follow-up	mg/dL or mUI/L
Change in fasting blood glucose level	From start of Norditropin® treatment until end of follow-up	mg/dL or g/L or mmol/L

Title of endpoint	Time frame	Unit
Change in fasting total cholesterol	From start of Norditropin® treatment until end of follow-up	mg/dl or g/L or mmol/L
Change in fasting triglycerides	From start of Norditropin® treatment until end of follow-up	mg/dL or g/L or mmol/L
Change in fasting HDL cholesterol	From start of Norditropin® treatment until end of follow-up	mg/dL or g/L or mmol/L
Change in fasting LDL cholesterol	From start of Norditropin® treatment until end of follow-up	mg/dL or g/L or mmol/L
Change in fasting total cholesterol/HDL ratio	From start of Norditropin® treatment until end of follow-up	NA
Change in inhibin B	From start of Norditropin® treatment until end of follow-up	pg/mL
Change in AMH	From start of Norditropin® treatment until end of follow-up	mg/mL
Change in LH (female from 8 years old and male from 9 years old)	From start of Norditropin® treatment until end of follow-up	mg/mL
Change in FSH (female from 8 years old and male from 9 years old)	From start of Norditropin® treatment until end of follow-up	UI/L or mUI/mL
Change in oestradiol (female from 8 years old and male from 9 years old))	From start of Norditropin® treatment until end of follow-up	pg/mL
Change in testosterone (female from 8 years old and male from 9 years old)	From start of Norditropin® treatment until end of follow-up	ng/mL

Secondary objective-3: To describe the therapeutic care of patients
 The endpoints related to the secondary objective-3 are listed in [Table 5](#).

Table 5 Secondary endpoints in relation to secondary objective 3

Title of endpoint	Time frame	Unit
Norditropin® treatment patterns		
Change in dose of Norditropin® treatment	From start of Norditropin® treatment until end of follow-up	mg/kg/day
Frequency of injections of Norditropin® treatment per week	From start of Norditropin® treatment until end of follow-up	Count of events
Number of modifications (change in dosage/ temporary stop)	From start of Norditropin® treatment until end of follow-up	Count of events
Reasons for treatment modifications	From start of Norditropin® treatment until end of follow-up	NA
Duration of temporary stop	From start of Norditropin® treatment until end of follow-up	Months

Title of endpoint	Time frame	Unit
Total duration of Norditropin [®] treatment	From start of Norditropin [®] treatment until end of follow-up	Years
Total cumulative dose of Norditropin [®] treatment	From start of Norditropin [®] treatment until end of follow-up	mg/kg
Other NS treatments		
Type and number of concomitant treatments	At all visits	Count of events
Type and number of concomitant treatments linked to an adverse event	At all visits	Count of events

Secondary objective-4: To describe the NS in terms of auxological characteristics, diagnosis and NS comorbidities.

The endpoints related to the secondary objective-4 are listed in [Table 6](#).

Table 6 Secondary endpoints in relation to secondary objective 4

Title of endpoint	Time frame	Unit
Auxological characteristics		
Change in weight	From start of Norditropin [®] treatment until end of follow-up	SDS
Change in body mass index (BMI)	From start of Norditropin [®] treatment until end of follow-up	Kg/m ²
Change in bone age	From start of Norditropin [®] treatment until end of follow-up	year
Change in height velocity	From start of Norditropin [®] treatment until end of follow-up	cm/year and SDS/year
Type and number of NS comorbidities	At all visits	NA

Secondary objective-5: To evaluate the evolution of Health-Related Quality of Life (HRQoL) of patients/Legally Acceptable Representative (LAR).

The endpoints related to the secondary objective-5 are listed in [Table 7](#).

Table 7 Secondary endpoint in relation to secondary objective 5

Title of endpoint	Time frame	Unit
Change in HRQoL score (PedsQL)	From start of Norditropin [®] treatment until end of follow-up	NA

